## 4.3 Dosing Rationale

The 2 arms of CVL-865 have been selected based on the first-in-human safety and tolerability data, the pharmacodynamic (PD) profile, and the efficacious doses used in the clinical photosensitive epilepsy Trial B7431005. Single doses up to 100 mg have been safe and well tolerated and associated with mild adverse effects. No changes in electrocardiograms (ECGs) or vital sign measurements have been observed at doses up to 100 mg. Multiple doses of CVL-865 up to 42.5 mg BID have been found to be safe and well tolerated in healthy adult subjects.

The top maintenance dose of 25 mg BID is designed to fully test the therapeutic potential of CVL-865 as adjunctive therapy in the treatment of focal onset seizures. At that dose level the steady-state exposure levels of CVL-865 are expected to be comparable with those at which the peak effects in saccadic peak velocity, a reliable biomarker of  $\alpha 2/3$  activity, were observed following single dose (65 mg) administration (Trial B7431001). Likewise, the exposure levels are expected to be comparable with those at which efficacy was observed in a single-dose (52.5 mg) photosensitive epilepsy trial (Trial B7431005).

The relationship between GABAA receptor occupancy in the whole brain and plasma exposure levels of CVL-865 was characterized in an open-label, single-dose (10 and 65 mg) trial in healthy volunteers (Trial B7431004). Pharmacodynamic analysis of the GABAA receptor occupancy data indicated that nearly complete (ie, >80%) receptor occupancy was achieved at the peak exposure level of the 65 mg dose. More specifically, with respect to  $\alpha$ 2 receptor occupancy within the brain, the 25 mg BID dosing regimen is anticipated to achieve steady-state exposure levels of CVL-865 within the range anticipated to produce approximately 80% receptor occupancy. In addition, pharmacokinetic (PK)/PD modeling of saccadic peak velocity and  $\alpha$ 2 receptor occupancy data also suggests that no additional benefit would come from increasing the dose above 25 mg BID.

The lower dose of 7.5 mg of CVL-865 administered BID is anticipated to result in exposures with limited overlap with the high dose and a submaximal effect based on the same neurofunctional endpoints described above. The 7.5 mg BID and 25 mg BID doses will facilitate evaluation of a wide exposure and target occupancy range in this trial to facilitate appropriate dose selection for future clinical trials. Exposures from both dosing regimens are not expected to exceed the no observed adverse effect level (NOAEL) established based on the pivotal 13-week toxicological studies in rats and dogs.

## 4.4 Definition of Completed Subject

Subjects continuing treatment with CVL-865-SZ-001 in the open-label extension trial are considered to have completed this trial if he/she has completed the Maintenance Phase of the trial (ie, completed Visit 4) as shown in the Schedule of Assessments.

Subjects not continuing in the open-label extension trial, are considered to have completed this trial if he/she has completed all phases of the trial including the last scheduled procedure (Day 120 phone contact) shown in the Schedule of Assessments.

## 4.5 End of Trial Definition

The end of the trial is defined as the date of the last visit (including phone contact) of the last subject in the trial globally.

## 5 TRIAL POPULATION

Prospective approval of protocol deviations to recruitment and enrollment criteria, also known as protocol waivers or exemptions, is not permitted.

A Seizure Identification and Diagnostic Review Form (SIF/DRF) will need to be completed by site personnel for every subject. This information will be faxed or emailed to The Epilepsy Study Consortium (TESC) after the Screening Visit for review and approval. The SIF/DRF will be used to ensure that the seizures are classified accurately, the subject is appropriate for the trial, and will help to confirm the diagnosis. Subjects cannot be enrolled until the TESC review and feedback of the SIF/DRF has been completed and the site personnel have received final notification.

## 5.1 Inclusion Criteria

Subjects are eligible to be included in the trial only if all of the following criteria apply:

1.	Male and female subjects, ages 18 to 75 years, inclusive, at the time of signing the ICF.
2.	A diagnosis of epilepsy with focal onset (as defined in the 2017 ILAE Classification of Seizures [Fisher et al, 2017]), focal aware (except subjects with only focal aware seizures without a motor component), focal impaired awareness, and focal to bilateral tonic-clonic seizures for at least 2 years prior to signing the ICF. Diagnosis will be based on the investigator's assessment of available clinical, radiographic, and EEG data and the review by TESC.
3.	A history of an average of 4 or more spontaneous and observable focal onset (as defined in the 2017 ILAE Classification of Seizures [Fisher et al, 2017]), focal aware (except subjects with only focal aware seizures without a motor component), focal impaired awareness, and focal to bilateral tonic-clonic seizures per 28-day period for at least 3 months (84 days) prior to signing the ICF.
4.	A minimum of 8 focal onset (as defined in the 2017 ILAE Classification of Seizures [Fisher et al, 2017]), focal aware (except subjects with only focal aware seizures without a motor component), focal impaired awareness, or focal to bilateral tonic-clonic seizures during the 8-week Baseline Period with no 21-day period free of any of these seizure types.
5.	Subjects who have tried and failed at least 2 appropriate AEDs in the past.
6.	Subjects currently taking 1 to 3 permitted AEDs (see concomitant medication exclusions) at a stable dose for 4 weeks prior to the Screening Visit. VNS, DBS, and RNS is permitted and is not considered an AED. The VNS, DBS, and RNS settings should remain stable for 4 weeks prior to the Screening Visit. Note: Should a subject require a change of AED therapy/dose or VNS, DBS, or RNS settings between the Screening Visit and Visit 1, that subject should not continue in the trial at that time but must remain on the new regime for at least 4 weeks and then may repeat the screening process.
7.	An MRI or CT scan of the head within 10 years prior to Screening Visit to demonstrate no progressive structural abnormality. If a scan is not available, one should be conducted during the Baseline Period with a report that demonstrated no progressive structural abnormality available prior to randomization.
8.	BMI of 17.5 to 40.0 kg/m  and a total body weight $>50$ kg (110 lbs).
9.	A female subject of childbearing potential (see Section 10.4, Appendix 4) who is sexually active with a nonsterilized male partner must agree to use a highly effective method of contraception (see Section 10.4, Appendix 4) from signing of informed consent throughout the duration of the study and for 30 days post last dose.
	A male subject with a pregnant or a nonpregnant partner of childbearing potential must agree to use condom during treatment and until the end of relevant systemic exposure in the male subject for 94 days following the last dose with IMP.
10.	Capable of giving signed informed consent as described in Section 10.1.3 (Appendix 1), which includes compliance with the requirements and restrictions listed in the ICF and in this protocol.
11.	Ability, in the opinion of the investigator, to understand the nature of the trial and comply with protocol requirements, including the prescribed dosage regimens, scheduled visits, laboratory tests, and other trial procedures.

Abbreviations: AED = anti-epileptic drug; BMI = body mass index; CT = computed tomography; DBS = deep brain stimulator; EEG = electroencephalogram; ICF = informed consent form; ILAE = International League Against Epilepsy; IMP = investigational medicinal product; MRI = magnetic resonance imaging; RNS = responsive neurostimulator; TESC = The Epilepsy Study Consortium; VNS = vagus nerve stimulator

## 5.2 Exclusion Criteria

Subjects are excluded from the trial if any of the following criteria apply:

Target I	Disease
1.	Subjects with (genetic) idiopathic generalized epilepsies or combined generalized and focal epilepsies, including a history of Lennox-Gastaut Syndrome.
2.	Subjects with only focal aware seizures without a motor component.
3.	Subjects with a history of seizures over the past 12 months that occur at such a high frequency they cannot be counted (eg, repetitive seizures, cluster seizures).
4.	Subjects with a history of psychogenic non-epileptic seizures within the year prior to signing the ICF.
5.	Subjects with a history of status epilepticus within 5 years prior to signing the ICF.
6.	Subjects with a history of neurosurgery for seizures less than 1 year prior to signing the ICF, or radiosurgery less than 2 years prior to signing the ICF.
Medical	History and Concurrent Diseases
7.	Subjects with a current history of significant cardiovascular, pulmonary, gastrointestinal, renal, hepatic, metabolic, hematological, immunological, or neurological (excluding focal onset epilepsy) disease that, in the opinion of the investigator or medical monitor, could compromise either subject safety or the results of the trial. In addition, subjects with a psychiatric illness of sufficient severity as to make them inappropriate for the trial are excluded.
	Medical conditions that are minor or well-controlled may be considered acceptable if the condition does not expose the subject to an undue risk of a significant AE or interfere with the assessments of safety or efficacy during the course of the trial. The medical monitor should be contacted in any instance where the investigator is uncertain regarding the stability of a subject's medical conditions(s) and the potential impact of the condition(s) on trial participation.
8.	Subjects with an active CNS infection, demyelinating disease, degenerative neurological disease or any CNS disease deemed to be progressive during the course of the trial that may confound the interpretation of the trial results.
9.	Subjects with a history of substance or alcohol-use disorder (excluding nicotine; DSM-5 criteria) within 2 years prior to signing the ICF.
10.	Subjects who answer "Yes" on the C-SSRS Suicidal Ideation Item 4 (Active Suicidal Ideation with Some Intent to Act, Without Specific Plan) and whose most recent episode meeting criteria for this C-SSRS Item 4 occurred within the last 6 months, OR
	Subjects who answer "Yes" on the C-SSRS Suicidal Ideation Item 5 (Active Suicidal Ideation with Specific Plan and Intent) and whose most recent episode meeting criteria for this C-SSRS Item 5 occurred within the last 6 months OR

	Subjects who answer "Yes" on any of the 5 C-SSRS Suicidal Behavior Items (actual attempt, interrupted attempt, aborted attempt, preparatory acts, or behavior) and whose most recent episode meeting criteria for any of these 5 C-SSRS Suicidal Behavior Items occurred within the last 2 years, OR									
	Subjects who, in the opinion of the investigator, present a serious risk of suicide.									
Physical	al Examination and Clinical Laboratory Results									
11.	Subjects who test positive for human immunodeficiency virus (HIV), hepatitis B and/or or hepatitis C infection.									
12.	Subject with a positive drug screen for illicit drugs are excluded and may not be retested or rescreened. Subjects with a positive urine drug screen resulting from use of marijuana (any cannabinoids), prescription, or over the counter medications or products that, in the investigator's documented opinion do not signal a clinical condition that would impact the safety of the subject or interpretation of the trial results may continue evaluation for the trial following consultation and approval by the medical monitor.									
13.	Subjects with a 12-lead ECG demonstrating either of the following:									
	• QT interval corrected for heart rate using Fridericia's formula (QTcF) >450 msec (average of 3 ECGs obtained at the Screening Visit assessed by central reader)									
	QRS interval >120 msec at the Screening Visit									
14.	Subjects with any of the following abnormalities in clinical laboratory tests at the Screening Visit, as assessed by the central laboratory and confirmed by a single repeat measurement, if deemed necessary:									
	• AST or ALT $\geq 2 \times ULN$									
	• Total bilirubin ≥1.5 × ULN. Subjects with a history of Gilbert's syndrome may be eligible provided the direct (conjugated) bilirubin is <uln< th=""></uln<>									
	• Females: Hemoglobin <11 g/dL; Males: hemoglobin <12 g/dL									
	
 
White blood cell (WBC) count <3.0 × 10^9/L
 
									
	• Neutrophil count $< 2.0 \times 10^9$ /L									
	• Platelet count $<150 \times 10^{9}/L$									
15.	Subjects with other abnormal laboratory test results, vital sign results, or ECG findings unless, based on the investigator's judgment, the findings are not medically significant and would not impact the safety of the subjects or the interpretation of the trial results. The medical monitor should be contacted to discuss individual cases, as needed.									
	Tests with exclusionary results should be repeated to ensure reproducibility of the abnormality before excluding a subject based on criteria provided in this protocol. For ECGs, 3 consecutive recordings are required and if 2 of the 3 remain exclusionary, then the subject is not eligible for the trial.									
Disallow	ed Prior and Concomitant Medications									
16.	Subjects receiving more than 3 background AEDs for their epilepsy.									
17.	Subjects taking BZD medication chronically or who require a BZD (oral, intramuscular, or suppository) as rescue medication for epilepsy for more than 4 days on average over a 28-day period. (Note: a rescue BZD will be permitted if used ≤4 days on average over a 28-day period). During the Screening/Baseline Period, subjects requiring a BZD (oral, intramuscular, or suppository) as rescue medication for epilepsy more than 4 days on average over a 28-day period will be excluded.									

18.	Subjects taking other prohibited medications prior to randomization (as listed in Table 6) or who would be likely to require the use of prohibited concomitant medications during the trial (as listed in Table 7).
19.	Subjects taking any drug that is strong or moderate inducer/inhibitor CYP3A4 metabolism, which has the potential to alter CVL-865 exposure levels (see Section 6.5).
20.	Subjects taking any drug that is a sensitive P-gp and BCRP substrate (see Section 6.5).
21.	Vigabatrin is excluded as a concomitant AED, unless subject has been taking it for at least 2 years prior to signing the ICF and have no evidence of visual field defects on at least 2 visual field tests within 6 months of signing the ICF.
22.	Felbamate is excluded as a concomitant AED, unless subject has been taking it for at least 2 years prior to signing the ICF, with a stable dose for $\geq$ 49 days, and have acceptable hematology and liver function test values (or discontinued felbamate no less than 49 days prior to signing the ICF).
Other	
23.	Female subjects who are breastfeeding and/or who have a positive pregnancy test result prior to receiving IMP.
24.	Any condition possibly affecting drug absorption, including bowel resections, bariatric weight loss surgery, or gastrectomy (this does not include gastric banding).
25.	Subjects with difficulty swallowing.
26.	Subjects who are known to be allergic or hypersensitive to the IMP or any of its components.
27.	Subjects who have participated in any clinical trial within 60 days prior to signing the ICF or who have participated in more than 2 clinical trials within the year prior to signing the ICF.
28.	Any subject who, in the opinion of the sponsor, investigator, or medical monitor, should not participate in the trial.

Abbreviations: AE = adverse event; AED = anti-epileptic drug; ALT = alanine aminotransferase; AST = aspartate aminotransferase; BCRP = breast cancer resistance protein; BZD = benzodiazepine; CNS = central nervous system; C-SSRS = Columbia – Suicide Severity Rating Scale; CYP = cytochrome P450; DSM-5 = Diagnostic and Statistical Manual of Mental Disorders, 5th edition; ECG = electrocardiogram; ICF = informed consent form; IMP = investigational medicinal product; P-gp = P-glycoprotein; ULN = upper limit of normal range.

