# 8.4.6.3 Abnormal Liver Function Tests

The finding of an elevated alanine aminotransferase (ALT) or aspartate aminotransferase (AST)  $>3 \times$  upper limit of normal range (ULN) in combination with either an elevated total bilirubin  $>2 \times$  ULN or clinical jaundice in the absence of cholestasis or other causes of hyperbilirubinemia is considered to be an indicator of severe liver injury. Therefore, investigators must report the occurrence of either of the following as an AESI to the sponsor with 24 hours:

- Treatment-emergent ALT or AST >3  $\times$  ULN and total bilirubin >2  $\times$  ULN
- Treatment-emergent ALT or AST  $>3 \times$  ULN in combination with clinical jaundice

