The number and percentage of subjects who have post-baseline elevations in liver transaminase (alanine aminotransferase [ALT] or aspartate aminotransferase [AST]) or bilirubin abnormalities in relation to fold above the upper limit of normal will be summarized according to the Food and Drug Administration's Premarketing Clinical Evaluation on Drug-Induced Liver Injury Guidance for Industry (FDA 2009). Abnormal hepatic laboratory values will be categorized and evaluated for any occurrence among all post-baseline assessments (where "and" in the bulleted list below indicates elevations occurring at the same visit). Within each laboratory parameter grouping, a subject may be counted once per elevation criteria using the worst-case result. That is, a subject with a worst case ALT elevation > 5 × the ULN would be counted once in the ALT > 3 × ULN category and once in the ALT > 5 × ULN category, regardless of how many ALT elevations the subject had that met the > 3 × ULN and > 5 × ULN elevation criteria.

- ALT and/or AST > $3 \times$ ULN and total bilirubin > 1.5 or $2 \times$ ULN
- AST > 3, 5, 10, $20 \times ULN$
- ALT > 3, 5, 10, 20 × ULN
- Total bilirubin $> 1.5, 2 \times ULN$
- Alkaline phosphatase (ALP) $> 1.5 \times ULN$

In addition, an eDISH plot, a shift plot showing liver safety panel tests over time (baseline vs. post-baseline), and distribution plots of ALT, AST, ALP, and bilirubin over time will be produced to aid identification of any potential cases (Merz M. et. al. 2014). The plots to be included are the scatter plot of maximum transaminase versus maximum bilirubin, the liver test safety panel over time, and the distribution of ALT by time. The distribution plots for AST, ALP, and bilirubin will use the same format as used for ALT.

Other tests (drug screen, pregnancy testing, serology) will be presented in listings.

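### SAP 5.14.3 liver counts for bilirubin, ALP and the combined row ignore baseline, so elevations that entry criteria allow are counted with on-study changes

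*Protocol*

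**What the plan says.** **Entry.** Protocol 5.2 item 14 excludes on "Total bilirubin ≥1.5 × ULN" at screening, then adds: "Subjects with a history of Gilbert's syndrome may be eligible provided the direct (conjugated) bilirubin is" below ULN. No upper bound on total bilirubin applies to these subjects. ALT or AST at or above 2 × ULN is also exclusionary. Item 14 does not name ALP. A raised ALP falls under item 15, which excludes "Subjects with other abnormal laboratory test results, vital sign results, or ECG findings unless, based on the investigator's judgment" they are unimportant for safety and interpretation, and under item 7, which excludes significant hepatic disease as judged by the investigator or medical monitor. Neither gives a number.

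**Counting.** SAP 5.14.3 states: "Abnormal hepatic laboratory values will be categorized and evaluated for any occurrence among all post-baseline assessments". The categories include total bilirubin above 1.5 and 2 × ULN, ALP above 1.5 × ULN, and ALT and/or AST above 3 × ULN together with total bilirubin above 1.5 or 2 × ULN at the same visit. No baseline condition is attached.

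**Other displays.** SAP 5.14.3 also plans shift tables of toxicity grade, listings of every result, an eDISH plot and a baseline-versus-post-baseline liver shift plot. SAP 5.14.1 summarizes adverse events of special interest (AESIs). Protocol 8.4.6.3 defines the liver AESI as treatment-emergent and says that the transaminase–bilirubin combination "in the absence of cholestasis or other causes of hyperbilirubinemia is considered to be an indicator of severe liver injury".

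**The concern.** For ALT and AST alone, the entry limit (below 2 × ULN) sits under the first reporting cut-off (3 × ULN), so a value allowed at screening cannot enter those rows unless it rises. Bilirubin and ALP lack that protection. The Gilbert's exception admits values above the table's own bilirubin cut-offs, and no number bounds ALP at entry.

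The by-arm counts for these rows can therefore mix subjects who were already above a cut-off before dosing with subjects who crossed it on treatment. With about 50 subjects per arm, two or three pre-existing cases are visible in such a table. In the combined row, a subject with Gilbert's syndrome needs only a transaminase rise, because the bilirubin half is already met.

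**Working it through.** The documents give no figure on this point, so there is none to reproduce. The check applies the SAP rules to values that entry permits, then illustrates size.

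**1. Which rows a subject enters.** Values are multiples of ULN. Grade bands come from SAP 9.6, which grades both tests on ULN only: bilirubin Grade 2 is above 1.5 to 3.0, and ALP Grade 1 runs from ULN to 2.5. The column for rows newly met counts a row only if it was not met at baseline.

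| Baseline → on study | SAP rows entered | Rows newly met | Shift-table entry |
|---|---|---|---|
| Bilirubin 1.8 → 1.8 | bilirubin >1.5 | none | Grade 2 → 2 |
| Bilirubin 2.2 → 2.2 | bilirubin >1.5, >2 | none | Grade 2 → 2 |
| ALP 1.8 → 1.8 | ALP >1.5 | none | Grade 1 → 1 |
| ALP 1.1 → 1.8 | ALP >1.5 | ALP >1.5 | Grade 1 → 1 |
| Bilirubin 2.2 throughout, ALT 1 → 3.2 | bilirubin >1.5, >2; ALT >3; both combined cut-offs | ALT >3; both combined cut-offs | bilirubin Grade 2 → 2 |
| ALT and AST 1.9 → 1.9 | none | none | not applicable |

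**2. What the shift table can separate.**

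- Bilirubin >1.5: yes, because the cut-off is the Grade 1/2 boundary.
- Bilirubin >2: no, because the cut-off lies inside Grade 2.
- ALP >1.5: no, because an unchanged 1.8 and a rise from 1.1 to 1.8 look identical.
- Combined row: no, because it has no shift table.

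The fifth case also shows that a plain not-met-at-baseline rule would still call the combined row new, although only ALT moved. That row needs its own flag.

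**3. Size, under assumptions.** The documents do not say how many subjects would be above a cut-off at baseline. Suppose n subjects are above it, stay above it, and fall into the three arms with probability 1/3 each. The probability that one given dose exceeds placebo by at least 2 is the sum of n!/(a! b! p!) / 3ⁿ over all splits with a − p ≥ 2, where a is the count on that dose, b on the other dose and p on placebo.

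For n = 3, the qualifying splits (a, b, p) are (3,0,0) with weight 1 and (2,1,0) with weight 3, so the result is 4/27 = 15%. The event that either dose exceeds placebo by at least 2 has twice that probability, 8/27 = 30%, because the two doses cannot both do so with only three subjects.

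| n (share of 150) | One given dose ≥2 above placebo | Either dose ≥2 above placebo |
|---|---|---|
| 0 or 1 | 0% | 0% |
| 3 (2%) | 15% | 30% |
| 6 (4%) | 23% | 39% |
| 9 (6%) | 27% | 44% |

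As a cross-check, take two arms of 50 with independent binomial counts and a prevalence of 1%, 2%, 5% or 10%. The expected number per arm is 0.5, 1, 2.5 or 5. The chance that the two arms differ by 2 or more in either direction is 12%, 26%, 48% or 61%.

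**The case against.** The strongest reply is that baseline is handled elsewhere. The shift tables, the liver shift plot and the full listings all show it, and the liver AESI is defined as treatment-emergent. With a handful of subjects, a reader could resolve each case from the listings. The SAP also describes its categories as post-baseline elevations, which is literally what it counts, and does not call them drug-related. This largely stands and keeps the severity low. What remains is that none of these displays splits the counts, and the shift grades separate only the bilirubin >1.5 row.

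Three stronger readings are tempting, and the documents do not support them:

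- **That the table is biased against the drug.** Randomization balances pre-existing elevations on average, so only chance imbalance is left. Safety summaries are descriptive, and even 2/50 against 0/50 gives a Fisher p-value of 0.49.
- **That Gilbert's syndrome alone puts a subject in a severe-injury row.** The SAP does not label the combined row that way, and entry still requires ALT or AST above 3 × ULN, which means a rise from a screening value below 2 × ULN.
- **That raised ALP is unrestricted at entry.** Items 7 and 15 partly screen it, though by judgment and without a number.

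It is also tempting to drop subjects already above a cut-off from the counts. That would lose real worsening: ALP going from 1.6 to 4 × ULN would leave the only ALP row, and a Gilbert's subject going from bilirubin 2.2 to 6 × ULN with ALT at 10 × ULN would leave the combined row.

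**Conclusion.** The point holds as a low-severity matter of presentation. As written, SAP 5.14.3 places unchanged, pre-existing elevations of bilirubin and ALP in the same by-arm counts as new ones. It also lets a pre-existing bilirubin supply half of the combined criterion. ALT-only and AST-only rows are not affected by values allowed at screening, and nothing in efficacy, alpha or sample size depends on this.

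The size is unknown. The percentages assume between 3 and 9 persistently raised subjects among 150, or a prevalence of 1% to 10%; the documents support no particular value, and zero is possible. For one pre-specified dose against placebo the relevant figures are 15% to 27%. The 30% to 44% figures apply only if the reader looks at whichever dose is higher. Eligibility item 14 is not at fault and need not change.

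**What to change.** In SAP 5.14.3, keep all any-occurrence counts as they stand. For the bilirubin, ALP and combined rows, add a split by baseline status:

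1. at or below the cut-off at baseline;
2. already above it and not worsened;
3. already above it and worsened from baseline by a pre-specified margin.

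For the combined row, base the split on the bilirubin component. In that row and on the eDISH plot, flag subjects with raised baseline bilirubin or a history of Gilbert's syndrome and show their direct bilirubin, which Protocol Appendix 2, Table 9 already includes. Remove no subject from the combined row.

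The cost is a short SAP addition, a few more table lines and one programming condition. The sponsor must choose the worsening margin before unblinding. No new data are needed.
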